7.2 Interim Analysis / Stopping Rule

This will be a two stage study. In stage 1, ten patients are enrolled in each arm. If 3 or more of the first 10 patients in an arm fail (i.e. have a “persistently elevated estradiol level” as defined in Section 3.1 Study Design), no more patients are enrolled in that arm and it is concluded that the treatment for that arm is not safe. Patients already enrolled in that arm will be notified and given the option of discontinuing treatment. In stage 2 an additional 25 patients are enrolled in the arms that were not closed after stage 1. A treatment is considered unsafe if a total of 5 or more patients in both stages have failed (i.e. have a “persistently elevated estradiol level” as defined above). Under the null hypothesis that the treatment is unsafe with true probability of failure (i.e. persistent elevation of estradiol above postmenopausal threshold) equal to 25% or greater, the probability of rejecting the null hypothesis falsely (i.e. concluding the treatment is safe when it is not) is 5%. Figure 1 shows the operating characteristic using this two stage design.

[figure not shown]

Figure 1. Operating characteristic for two-stage safety trial.

7.3 Secondary Outcomes Statistical Analysis

A secondary outcome variable in this study is the change in the scores on the CARES Sexual Dysfunction Subscale from baseline to week 12 within each patient treatment group. The ESTRING and testosterone cream treatment groups will be analyzed independently. Another secondary outcome variable will be the difference in the change in CARES Sexual Dysfunction Subscale from baseline to week 12 between the ESTRING and testosterone cream treatment groups.

Based on results from previous studies investigating menopausal symptoms and sexual dysfunction in breast cancer survivors published by Ganz (11, 39), mean scores on the CARES Sexual Dysfunction Subscale (SDS) was 1.35 ± 1.13 for one group and 1.53 ± 1.17 for the other group (on a scale on 0-4). Within patient correlations were not published in either of these studies, but we would expect it to be 0.8 or greater. The formula for the sd when comparing 2 correlated measurements is: $\text{sd of difference} = \sqrt{2*\text{sd}^2*(1 - \text{cor})}$.

Based on a standard deviation of 1.17 from a study of different patients, a table for the $\text{sd}(\text{diff})$ as a function of the correlation is:

corr	$\text{sd}(\text{diff})$
0.7	0.91
0.8	0.74
0.9	0.52

With 35 evaluable patients in each treatment group (ESTRING and testosterone cream), we will have 90% power to detect an improvement of 0.41 when the correlation is 0.8, based on a two-sided paired t-test at 5% level of significance. This translates to a reduction from 1.53 to 1.12 for treated patients.

Using a two-sample t-test, and with 35 evaluable patients in each treatment group, we would have 80% power to detect a difference of 0.57 in the change scores (e.g. a reduction of 0.1 in one group vs. a reduction of 0.67 in the other group). Currently, there is no published research to suggest an expected effect size for these interventions. However, after carrying out this trial we will have estimates for the reduction for each treatment type and could use these estimates to plan a larger study to determine if one intervention is actually superior to the other.

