The trial is designed to test the null hypothesis that a treatment is unsafe (25% or more of patients have a persistently elevated estradiol above the postmenopausal range) at a 5% level of significance. The alternate hypothesis is that a treatment is safe (i.e. fewer than 25% of patients have a persistently elevated estradiol above the postmenopausal range). Each treatment arm is tested separately. The trial is designed to have 98% power of concluding that a treatment is safe if the true failure rate is 5% and 70% power when the true failure rate is 10%.

Secondary Outcomes

A secondary outcome variable is the change in scores on the CARES Sexual Dysfunction Subscale from baseline to week 12. The ESTRING and testosterone cream treatment groups will be analyzed independently. A paired t-statistic will be used to compare week 12 to baseline values. With 35 patients in each treatment group (ESTRING and testosterone cream), we will have 90% power to detect an effect size of 0.41 based on a two-sided paired t-test at 5% level of significance.

Another secondary outcome variable will be the difference in the mean change in CARES Sexual Dysfunction Subscale from baseline to week 12 between the ESTRING and testosterone cream treatment groups. Using a two-sample t-test, and with 35 patients in each treatment group, we would have 90% power to detect a difference of 0.57 in the change scores (e.g. a reduction of 0.1 in one group vs. a reduction of 0.67 in the other group). Currently, there is no published research to suggest an expected effect size for these interventions. However, after carrying out this trial we will have estimates for the reduction for each treatment type and could use these estimates to plan a larger study to determine if one intervention is actually superior to the other.

TABLE OF CONTENTS

Section No.	Page No.
Protocol Title Page	1
Protocol Synopsis	3
Table of Contents	6
1.0 Introduction	8
1.1 Background	8
1.2 Rationale for this study	12
2.0 Study Objectives	13
2.1 Primary Objective	13
2.2 Secondary Objectives	13
3.0 Study Plan and Procedures	14
3.1 Overall study design	14

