3. STUDY PLAN AND PROCEDURES

3.1 Overall study design

This will be a single institution open label randomized Phase II study evaluating intravaginal testosterone cream vs. the Estring for vaginal dryness and/or decreased libido in early breast cancer patients treated with an aromatase inhibitor. Up to 80 early stage breast cancer patients will be enrolled over 36-48 months in order to have a total of 70 evaluable patients. To be considered evaluable, patients must complete their baseline evaluation and week 4 safety blood draw. Randomization of patients will attempt to balance the number of patients in each group based on self reported or medically documented depression, use of antidepressants, and relationship status (single vs. partnered). Patients will be randomized to a 12 week course of treatment with either:

- Testosterone Cream 1% micronized in velvachol - 0.5 gm of cream vaginally 3 times a week for total of 12 weeks of treatment
- Estring 2mg ring inserted vaginally once every 12 weeks

Patients will complete quality of life surveys including the CARES Sexual Interest and Sexual Dysfunction Subscales (Appendix A), which includes a single item sexual satisfaction measure previously tested by Ganz, at day 1 (baseline), week 4, and at the end of week 12 (the survey may be done either in the clinic, or at home and then mailed/faxed). Patients will undergo a gynecologic exam at baseline and at the end of week 12 (or sooner if they withdraw from the study or experience unexpected side effects). During this exam, the vaginal epithelium will be assessed using a 3-point scale evaluating color, petechiae, friability and dryness (Appendix B). Within each treatment group, composite scores of the vaginal epithelium at baseline will be compared to composite scores at study termination.

Serum estradiol assays sent to the UCSF clinical laboratory are sent out to Quest Diagnostics, which uses extraction chromatography RIA for their ultra-sensitive estradiol. Day 1 and week 4 samples will also be stored temporarily and then sent in batches to a specialized research lab which has developed an assay to quantify low levels of estradiol found in post-menopausal women. This assay is a radioimmunoassay after ether extraction, and has a sensitivity limit of 3pmol/l. Serum testosterone levels will also be sent to Quest, which uses an ultrasensitive testosterone measurement which is run by liquid chromatography tandem mass spectrometry.

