3.3.6 Replacement Policy

Patients who do not initiate study assigned therapy after signing consent or do not complete the week 4 blood draw for safety evaluation will be considered unevaluable and will be replaced.

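### The 90% power figures for CARES need 35 baseline-to-week-12 pairs per arm, but the 35 evaluable patients are counted at week 4 and no later loss is allowed for

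*Protocol*

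**What the plan says.** Section 7.3 of the protocol names as a secondary outcome "the change in the scores on the CARES Sexual Dysfunction Subscale from baseline to week 12 within each patient treatment group". A second outcome compares that change between the arms. For the within-arm comparison it states "With 35 evaluable patients in each treatment group (ESTRING and testosterone cream), we will have 90% power to detect an improvement of 0.41", at a correlation of 0.8 and "based on a two-sided paired t-test at 5% level of significance". The synopsis repeats 90% and 0.41 with 35 patients per group.

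For the between-arm comparison the two places differ. The synopsis says that "with 35 patients in each treatment group, we would have 90% power to detect a difference of 0.57 in the change scores". Section 7.3 gives 80% for the same difference of 0.57 and the same 35 per group.

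Section 3.1 fixes the meaning of evaluable: "To be considered evaluable, patients must complete their baseline evaluation and week 4 safety blood draw". Section 3.3.6 says that patients who do not start their assigned therapy or "do not complete the week 4 blood draw for safety evaluation will be considered unevaluable and will be replaced". Neither section requires a week 12 visit or a week 12 questionnaire. The only margin for loss is the enrolment of up to 80 patients to obtain 70 evaluable ones, and it is tied to that week 4 definition.

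**The concern.** The week 4 definition was written for estradiol safety monitoring. The CARES power statements borrow the resulting 35 per arm, although their endpoint falls eight weeks later. A patient who drops out at week 6, or never returns her week 12 form, still fills one of the 35 places and is not replaced. So 35 is the largest number of baseline-to-week-12 pairs that the evaluable group can supply, not an expected number.

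What is at stake is how the CARES results are read. Section 7.3 plans to use the estimates to design a larger study. If fewer than 35 pairs per arm are available, a non-significant change carries less weight than a printed 90% suggests.

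**Working it through.** **Inputs**
- SD of a single score: 1.17 (section 7.3: "Based on a standard deviation of 1.17 from a study of different patients").
- Within-patient correlation: 0.8 (section 7.3: "Within patient correlations were not published in either of these studies, but we would expect it to be 0.8 or greater").
- Differences: 0.41 within arm, 0.57 between arms.
- Two-sided 5% level. Section 7.3 states this for the paired test; it is taken to apply to the two-sample test as well.
- Patients per arm: 35.
- Loss between week 4 and week 12: not given in the protocol. A range of 0% to 20% is assumed.

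**Step 1: SD of the change score**

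SD(diff) = √(2 × 1.17² × (1 − 0.8)) = 0.740, which agrees with the 0.74 in the section 7.3 table.

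**Step 2: reproduce the plan's figures at 35 per arm**

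Within arm, noncentrality = (0.41/0.74) × √35 = 3.278 on 34 degrees of freedom. Power is 88.95% by noncentral t and 90.6% by the normal approximation. The stated 90% is reproduced.

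Between arms, noncentrality = (0.57/0.74) × √(35/2) = 3.222 on 68 degrees of freedom. Power is 88.8%. That agrees with the synopsis's 90% and not with section 7.3's 80%.

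**Step 3: reduce the number of pairs**

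The same formulas with n pairs per arm give:

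| Pairs per arm | Assumed loss after week 4 | Power, 0.41 within arm | Power, 0.57 between arms | Within-arm change detectable at 90% |
|---|---|---|---|---|
| 35 | 0% | 89.0% | 88.8% | 0.417 |
| 33 | 5% | 87.0% | 86.9% | 0.431 |
| 31 | about 11% (4/35) | 84.7% | 84.7% | 0.445 |
| 28 | 20% | 80.7% | 80.8% | 0.470 |

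The between-arm difference detectable at 90% rises from 0.582 with 35 per arm to 0.619 with 31.

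**Step 4: which statements are exposed**

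The within-arm 90% (section 7.3 and synopsis) and the synopsis's between-arm 90% have no margin: exact power is already about 89% with no loss. Section 7.3's between-arm 80% is still met at 28 per arm.

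**The case against.** The power sentence in section 7.3 is explicitly conditional on 35 evaluable patients and a correlation of 0.8, and under those conditions it reproduces. There is no arithmetic error in it. That stands.

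A reader might infer that the number analysed will fall below 35 and that 90% power will not be delivered. The documents do not support that as a fact. They give no loss rate after week 4. The gap between 80 and 70 is an enrolment ceiling that also covers patients who never start therapy, so its 12.5% (10/80) is not a dropout rate for treated patients.

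The protocol also limits the loss. The visit table in section 3.2 schedules quality-of-life questionnaires at early withdrawal, section 3.3.5 asks patients who stop early to attend a termination visit with the week 12 procedures, and section 3.1 lets forms be mailed or faxed. This deserves credit but does not remove the point. Patients are only asked to attend, and the protocol does not say that an early-withdrawal score stands in for week 12. The CARES items in Appendix A refer to the past 4 weeks, so an early form covers a different period from the one the endpoint names.

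The correlation may be better than 0.8, since the protocol expects 0.8 or greater. At 0.85, 28 pairs still give 90.4% within arm. But 0.8 is the stated basis for the 90%, the value is unpublished, and the table in section 7.3 also shows 0.7.

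Finally, CARES is secondary, and the 10 plus 25 patients per arm come from the two-stage estradiol rule. That limits the weight of the point and is the reason not to ask for more patients.

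**Conclusion.** The point holds as a mismatch between the population behind the power statements and the population with the endpoint. The 90% for a within-arm change of 0.41, and the synopsis's 90% for a between-arm difference of 0.57, require all 35 patients per arm to have CARES scores at both baseline and week 12. The evaluability and replacement rules do not secure this, and no allowance is stated.

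The size is moderate and conditional: 2 points of power at 5% loss, about 4 at 31 pairs and about 8 at 20% loss, measured from the exact 89%. These figures rest on an SD of change of 0.74, a correlation of 0.8, equal loss in both arms and an assumed loss rate.

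It would go too far to say that all the CARES power claims fail, because section 7.3's 80% between arms holds down to 28 per arm. That 80% does, however, contradict the synopsis's 90% for the same difference and number of patients.

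**What to change.** In section 7.3 and the synopsis, state CARES power for the expected number of patients with both baseline and week 12 scores, and label the loss after week 4 as an assumption. For example: 'Assuming 31 baseline and week 12 pairs per arm, power is about 85% for a within-arm change of 0.41 and about 85% for a between-arm difference of 0.57; 90% power is reached at 0.45 and 0.62.'

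Give the same between-arm figure in both places. With 35 pairs per arm and an SD of 0.74, the calculation yields about 89%.

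Leave the enrolment target and the estradiol definition of evaluable as they are. The cost is wording only, with no added patients. The stated within-arm power and the synopsis's between-arm power become a few points less favourable; section 7.3's between-arm figure would rise from 80% to about 85% under the same assumption.

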Up to 80 patients will be randomized to receive either testosterone or ESTRING so that 35 evaluable patients will receive each treatment. Randomization will attempt to balance the number of patients in each group based on self reported or medically documented depression, use of antidepressants, relationship status (single vs. partnered). Estradiol will be measured at baseline, at 4 weeks, and at 12 weeks into the study. If a patient is subsequently found to have a serum estradiol level outside of the post-menopausal range on day 1 of the study before the intervention begins (despite having a post-menopausal value during screening labs), this patient will be allowed to stay on study, and the subsequent estradiol level must be > 10 pg/ml higher than the baseline value to be considered a significant elevation outside the post-menopausal range. If a patient has an estradiol level outside of the post-menopausal range on the week 4 draw, or if there is a > 10 pg/ml increase in estradiol levels in patients with a baseline value above the post-menopausal range as described previously, they will have an additional lab draw at week 8.

Statistical methods

The primary outcome variable for determining safety at the end of the study is serial serum estradiol measurement. The test statistic is the number of patients that have a persistently elevated estradiol level above the post-menopausal range as described above. In the medical literature, there are no data to suggest what is “safe” or “unsafe” in terms of postmenopausal breast cancer patients being exposed to levels of estrogen above the postmenopausal range for a short duration of time (such as 12 weeks). No data exist to suggest that short term exposure to levels of estrogen above the post-menopausal range for up to 12 weeks would impact breast cancer recurrences. Therefore, it is fairly arbitrary to conclusively state that a certain rate of patients experiencing a short term increase in estradiol exposure with either of the treatment interventions (ESTRING or testosterone cream) is safe or unsafe. Taking this into consideration and after consulting with a number of breast cancer experts, we will consider each intervention “safe” if no more than 25% of patients in each arm have persistently elevated serum estradiol levels above the postmenopausal range after exposure to either of the study interventions.

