Review of the literature on management of vaginal symptoms in post-menopausal women identifies several therapies that appear to be effective in improving or eliminating vaginal dryness and decreasing dyspareunia. Non-hormonal vaginal moisturizers have been shown to relieve urogenital symptoms, but are not as effective as vaginal estrogens in randomized trials (14). A multicenter, open-label, randomized, parallel-group study compared the efficacy and safety of 25-microgram 17beta-estradiol vaginal tablets (Vagifem) with 1.25-mg conjugated equine estrogen vaginal cream (Premarin Vaginal Cream) for the relief of atrophic vaginitis in 159 post-menopausal women (15). Both treatments provided equivalent relief of the symptoms of atrophic vaginitis based on composite scores of vaginal symptoms (dryness, soreness, and irritation). At weeks 2, 12, and 24, increases in serum estradiol concentrations and suppression of follicle-stimulating hormone were observed in significantly more patients who were using the vaginal cream than in those who were using the vaginal tablets ($p < 0.001$). Vaginal tablet therapy resulted in greater patient acceptance and lower withdrawal rates compared with vaginal cream therapy. In a double-blind placebo-controlled, 1612 post-menopausal patients with urogenital complaints were randomized to receive the Vagifem insert or placebo tablet once a day over a period of 2 weeks, and then twice a week for a total of the 12 months (16). The overall success rates of Vagifem vs. placebo on subjective and objective symptoms of vaginal atrophy were 85.5%, and 41.4%, respectively. A significant improvement of urinary atrophy symptoms was also seen in the Vagifem treated group as compared with the beginning of the study (51.9% vs. 15.5%, $P=0.001$). Therapy with the Vagifem insert did not raise serum estrogen level nor stimulated endometrial growth in this study.

An estradiol releasing vaginal ring (Estring) has been compared to a topical estriol cream (Synapause) in a 12 week treatment study in postmenopausal women. The Estring was found to be well tolerated, produced equivalent results in reducing vaginal symptoms, and was preferred by patients as less messy and easier to use (17). Clinical trials with Estring have shown that there is minimal systemic absorption of estradiol and the range of serum estradiol

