This study will evaluate the safety and tolerability of the ESTRING and 1% testosterone cream administered vaginally as treatments for vaginal dryness and/or decreased libido in women receiving an aromatase inhibitor for Stage I-III breast cancer. This study will serially measure serum estradiol and testosterone levels in breast cancer patients being treated the ESTRING and 1% testosterone cream. The primary objective is to evaluate the safety of these treatments by determining whether an unacceptable number of patients receiving either of these treatments are found to have serum estradiol level outside of the post-menopausal range using standard clinical laboratory measurements. This study will also explore whether either of these treatments are effective in improving gynecologic or sexual quality of life in this patient population. This study may answer a number of important questions regarding these therapies which have not been well-investigated. If either of the treatments is found to be effective, and their short term safety and tolerability are confirmed in this study, further examination into the management of the difficult and increasing problem of urogenital atrophy and decreased libido in breast cancer survivors will be encouraged. Furthermore, improvements in the management of side effects associated with aromatase inhibitor treatment should lead to improved patient compliance, decreased discontinuation of treatment, and better outcomes.

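### The between-arm CARES comparison is planned as an unadjusted t-test on change scores, which is valid but less precise than an ANCOVA on data already collected

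*Protocol*

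**What the plan says.** Protocol section 7.3 defines two secondary outcomes on the CARES Sexual Dysfunction Subscale. One is the change within each arm, tested with a two-sided paired t-test. The other compares the arms: "Another secondary outcome variable will be the difference in the change in CARES Sexual Dysfunction Subscale from baseline to week 12". The only method named for the second is in the power statement that begins "Using a two-sample t-test, and with 35 evaluable patients in each treatment group". The synopsis names the same test, and neither place mentions a covariate.

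Section 3.1 says of the allocation: "Randomization of patients will attempt to balance the number of patients in each group based on self reported or medically documented depression". It lists antidepressant use and relationship status as the other two factors. The CARES questionnaire is completed at day 1, week 4 and week 12, so every patient should have a baseline score.

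The trial has two active arms, is open label and has no untreated or placebo group. Section 1.2 presents effectiveness as a question to explore, but it also contains the clause "If either of the treatments is found to be effective" as a condition for encouraging further work.

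**The concern.** A change score subtracts the whole baseline value, which amounts to fixing the regression slope of week 12 on baseline at 1. When the within-patient correlation is below 1 and the SD is the same at both visits, the best slope is the correlation itself. Fixing it at 1 then leaves avoidable variance in the comparison. It also lets a chance baseline difference between the arms leak into the result, in favor of the arm that starts worse.

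The balancing factors were presumably chosen because they matter for the outcome. Section 1.1 reports depression as a determinant of low desire, and links antidepressants to arousal and orgasm problems. Arousal and orgasm are two of the four items in the subscale (Appendix A). If the factors are prognostic, a test that ignores them after balancing on them has too large a standard error.

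What is at stake is precision in a small trial whose estimates are meant to plan a larger one. A second, separate issue is what the within-arm tests can show when no group goes untreated.

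**Working it through.** **Inputs.** From section 7.3: SD of a single score 1.17, expected within-patient correlation r of 0.8 or greater (not published; the table covers 0.7, 0.8 and 0.9), 35 evaluable patients per arm, difference 0.57. The two-sided 5% level is stated for the paired test and assumed here for the two-sample test. The SD is taken as equal at both visits, as the protocol's formula does.

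**Reproducing the protocol's figures.** SD of change = 1.17 × √(2(1 − r)) gives 0.906, 0.740 and 0.523, which matches the table. For the paired test, 0.41 ÷ (0.74/√35) = 3.28 on 34 df, and power is 89.0% by the noncentral t (90.6% by the normal approximation), so the stated 90% stands. For the two-sample test at r = 0.8, the standard error is 0.740 × √(2/35) = 0.177 and 0.57 ÷ 0.177 = 3.22 on 68 df. Power is 88.8% (89.7% by the normal approximation). This agrees with the synopsis ("we would have 90% power to detect a difference of 0.57 in the change scores") but not with section 7.3 ("we would have 80% power to detect a difference of 0.57 in the change scores"). That conflict is a separate matter; the comparison below uses the recomputed values.

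**Baseline-adjusted analysis.** Residual SD = 1.17 × √(1 − r²). The ratio of adjusted to change-score variance is (1 − r²) ÷ (2(1 − r)) = (1 + r)/2. Power for 0.57, with 67 df after adjustment:

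| r | SD, change | SD, adjusted | Variance ratio | Power, change | Power, adjusted |
|---|---|---|---|---|---|
| 0.7 | 0.906 | 0.836 | 0.85 | 73.7% | 80.3% |
| 0.8 | 0.740 | 0.702 | 0.90 | 88.8% | 91.7% |
| 0.9 | 0.523 | 0.510 | 0.95 | 99.4% | 99.6% |

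At r = 0.8, the difference detectable with 90% power falls from 0.582 to 0.552.

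**Adding the three balancing factors.** With no prognostic value assumed for them, the df drop to 64 and power is 80.3% at r = 0.7 and 91.7% at r = 0.8. The cost is therefore negligible. The benefit cannot be computed, because the protocol gives no figure linking these factors to CARES.

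**Chance imbalance.** The standard error of the baseline difference between arms is 1.17 × √(2/35) = 0.28. An imbalance of that size moves the change-score contrast by (1 − r) × 0.28, which is 0.06 at r = 0.8 and 0.08 at r = 0.7. Adjustment removes this.

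**Within-arm tests, as illustration only.** With SD of change 0.74 and n = 35, assumed non-treatment shifts of 0.20, 0.30 and 0.41 points would be significant 34%, 64% and 89% of the time. The protocol gives no estimate of such a shift on CARES.

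**The case against.** The t-test is named in a power statement, and covariates are often settled in an analysis plan, which is not at hand. This has some weight. Even so, it is the only between-arm method given in a section devoted to analysis of the secondary outcomes, and the synopsis repeats it. An ANCOVA introduced later would depart from the one test the protocol names.

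The test is also valid. A change score already contains the baseline value, so baseline is not ignored; what is missing is regression adjustment. No bias over repeated randomizations and no inflation of the type I error follows. If the balancing factors are prognostic, the test errs on the conservative side. The gain is modest at the correlation the protocol expects, about 3 points of power at 0.8, and almost nil at 0.9. All of this stands and limits the point to an improvement in efficiency.

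On the within-arm tests, a reader might infer that uncontrolled comparisons are left to carry an efficacy claim. The documents do not support that: the primary objective is safety, effectiveness is to be explored, a between-arm comparison is also planned, and the stated consequence of a good result is further study.

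A reader might also take the section 1.1 result, "The overall success rates of Vagifem vs. placebo on subjective and objective symptoms of vaginal atrophy were 85.5%, and 41.4%, respectively", as the size of the placebo response to expect here. It is a success rate for atrophy symptoms in postmenopausal women in a 12-month tablet trial. It is not a 12-week CARES change in women on aromatase inhibitors, and it does not transfer. Likewise, a non-treatment shift of 0.41 points is only the protocol's detectable difference under another name. Patients enter because of complaints, not a CARES cut-off, so regression to the mean on CARES cannot be sized either.

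Finally, ANCOVA between two active arms informs only on relative effect and cannot supply the missing control. That is correct, and it is why the two parts need separate remedies.

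**Conclusion.** The point holds as an efficiency improvement to a valid secondary analysis. Baseline adjustment lowers the variance by 15%, 10% and 5% at correlations of 0.7, 0.8 and 0.9, and raises power for a difference of 0.57 by about 6.6, 2.9 and 0.2 points. The gain is largest where the protocol's guess at the correlation proves optimistic. These figures assume equal SDs at both visits, a linear relation between baseline and week 12, and 35 patients per arm with week-12 scores. The extra gain from depression, antidepressant use and relationship status is plausible but cannot be quantified.

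The secondary point is one of interpretation. Without an untreated group, a significant within-arm change cannot be separated from placebo response, passage of time or regression to the mean, so it cannot by itself show that a treatment works. The protocol does not size these effects, and no size is claimed here.

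**What to change.** In section 7.3 and the synopsis, replace the two-sample t-test on change scores with an ANCOVA of the week-12 CARES Sexual Dysfunction score on arm, baseline score, depression, antidepressant use and relationship status. Report the adjusted difference between arms with its 95% confidence interval. The unadjusted change-score comparison can stay as a supporting analysis.

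Describe the within-arm changes as exploratory, uncontrolled estimates with 95% confidence intervals. State in section 7.3 that they will not be used alone to conclude that a treatment is effective, and bring the clause in section 1.2 into line with this.

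The cost is a few sentences and four degrees of freedom (68 to 64). All covariates are baseline data or randomization factors, so no new data are needed and the sample size does not change.
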